## 4.0 Study Endpoints\*

### 4.1 Primary endpoint

The primary endpoints of this pilot trial are:

1) Feasibility: We will determine the optimal strategy to achieve a high retention rate and adherence to the study protocol. We will also assess retention rates (proportion of included patients completing T2 follow up; we will target >70%), fidelity to the study protocol (Borrelli et al criteria; we will target >90%) and the Feasibility of Intervention Measure (FIM, 4 items, see Appendix 1. 3-month Follow Up Assessment (T2); we will target an average score of >3).

2) Acceptability: We will determine the acceptability of the AUDIO intervention and study protocol by assessing the proportion of patients and clinicians who agree to take part in the project and proportion of patients who listen to the recording. Our primary indicator of acceptability will be the recruitment of 108 participants (N=30 patients and 6 clinicians per site) over our planned data collection period of six months. We will determine the listening rates (we will target >70%): this will include the proportion of patients in the intervention arm that log in to the online system and listen to (and how often) the recording. We will also document the number of patients who share or report sharing the recording and caregivers who access the recording. Participants will complete the Acceptability of Intervention Measure (AIM, 4 items, see Appendix 1. 3-month Follow Up Assessment (T2); target an average score of >3).

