In both instances the patient and clinician can choose to stop or start the recording at any time by indicating this to the RA or stopping the recording device directly (e.g. where RA is outside of the room). The RA will schedule a time to meet with the patient via web conference, by phone or in person separate from the clinic visit, during which the RA will follow standardized instructions demonstrating how to access recordings. Pre- and post-visit surveys will be administered remotely, by email or telephone, for patients having telehealth visits.

The research team will maintain a copy of all recordings locally on a secure, HIPAA

PROTOCOL TITLE: *The impact of sharing audio recorded clinic visits on self-management in older adults: a multisite trial*

compliant server, captured by a second recorder, which will also serve as a back-up; once transferred to the server, the recording will be deleted from the digital recorder. Patient **access to recordings** will be possible via a secure web-based platform: HealthPAL.

HealthPAL. All patients with access to email will be able to access their recording online. The recording and sharing of the recorded data will be facilitated via HealthPAL, an online platform developed by PI [name] at Dartmouth (Appendix 4. HealthPAL system). The RA will register the patient in the HealthPAL system. Within the system they can record visits, which can then be accessed later online at home. The RA will demonstrate how to access and playback the recording on a computer or smartphone using each patient's unique login information. Access details (web address, login and use instructions) will be shared with patients both by email and on paper.

HealthPAL is a web application that runs on Amazon's cloud infrastructure (AWS). The root account under which the application is hosted is owned by Dartmouth College, which has a Business Associates Agreement (available upon request) in place with Amazon for the use of Amazon's HIPAA-eligible cloud services with Protected Health Information. All cloud services used by HealthPAL are covered under this agreement (Appendix. 5 HealthPAL security document).

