**5.1.1 Listening regime:** We will instruct patients to listen to their most recent recording both within 24 hours after their visit (as a means to reinforce and recall self-management information discussed), at one week (to reinforce learning) and within three days prior to their next visit (to identify information that needs clarification orgaols of care they would like to raise with their clinician). A reminder to listen to the recording will be sent to patients by email and/or text message (Appendix 24. Patient HealthPAL Reminder Emails). Patients will have the option of providing the contact information (email) of a family member, or caregiver who typically assists, or is involved in their care, and the study team will send this person access to the recording via the website.

**5.1.2 Recording future visits:** The RA will review the EMR of participants and document in REDCap scheduled patient visits (up to 6 months from recruitment). For patients in the AUDIO group, the RA will also attend each visit and assist with recording as described above, and administer the IPC survey post visit. While patients in the UC group have no further in clinic procedures following baseline assessment, we will plan to attend these visits when possible and offer participants the opportunity to complete the IPC survey post visit. We anticipate that patients will have one additional scheduled clinic visit over the 3-month period based on the average number of visits of these types of patients estimated from EMR data at each clinic site in 2017. We will neither record nor conduct follow-up assessments of unscheduled/urgent or acute visits so as to

PROTOCOL TITLE: *The impact of sharing audio recorded clinic visits on self-management in older adults: a multisite trial*  
minimize burden on both participants and study staff.

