#### 17.1.1 Feasibility (Aim 1.1)

PROTOCOL TITLE: *The impact of sharing audio recorded clinic visits on self-management in older adults: a multisite trial*

We will determine the optimal strategy to achieve a high retention rate and adherence to the study protocol. We will also assess retention rates (proportion of included patients completing T2 follow up; we will target >70% retention), the Feasibility of Intervention Measure (4 items; we will target an average score of >3), and high fidelity to the study protocol (Borelli et al criteria). Reasons for low-recruitment rates (e.g., eligibility criteria restrictions, participant refusal (and reason why, if available), and losses to follow-up) will be gathered as part of the fidelity checklist. If we fall short of targeted thresholds, we will determine the need for deviations from the existing study protocol. We will also gather data on management resources required to conduct the trial i.e., time required to recruit participants, and field notes on any idiosyncratic issues that arise at each site that will be documented and reported to site PIs.

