**17.3.1 Training:** All members of the research team and clinic staff will be trained in the study protocol and will have completed appropriate CITI training. The MPIs and research staff will meet weekly by WEBEX, from the time of study award, to plan protocol implementation at each site. Additionally, in month 6, a two-day 'kick off' training event will be hosted at Dartmouth College, and all study team members will join in person and/or virtually. During this training event, we will review and train research coordinators and assistants in all aspects of the study protocol including identification of patients, screening administration, recruitment and consent, survey administration and follow-up calls and plans for unexpected events. All RAs and site leads/coordinators will receive training in the identification, recruitment, consent, intervention and assessment administration. Training will involve role-play and feedback, as well as piloting of the entire recruitment process supervised by site PIs at each clinic.

**17.3.2 Protocol Adherence:** A fidelity checklist will be used (see Appendix. 16 Fidelity Checklist) to ensure the standard delivery and receipt of the audio recording. RAs will complete the checklist during initial recruitment and interim follow-up visits, documenting deviations from protocol and reasons. Site PIs will administer the fidelity checklist on 10% of the sample (approximately 3 patients per site), checking for 1) protocol adherence and 2) high agreement between their fidelity assessment and the RAs. Deviations from the protocol will be reported to the PIs and a mitigation plan developed during the weekly PI meeting. Participants from all sites will be given the option to contact the Dartmouth-Hitchcock Health (D-HH) Human Research Protection Program (HRPP), if they are dissatisfied or concerned about any aspect of the project; this information will be shared in the consent form.

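### Fidelity of audio delivery is scored by the research assistant who delivers it, and the Site-PI repeat is sized on both arms with no selection rule, so it would reach only about 1.5 AUDIO patients per site if selection ignores arm

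*Combined protocol and SAP*

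**What the plan says.** Section 4.1 lists fidelity to the study protocol among the primary feasibility measures, judged by published fidelity criteria with a percentage threshold ("criteria; we will target >90"). It names no arm, no scoring unit (patient, visit or item) and no denominator. Section 17.1.1 repeats the endpoint as "high fidelity to the study protocol", without the figure.

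Section 17.3.2 describes the instrument. The checklist is used "to ensure the standard delivery and receipt of the audio recording". On who fills it in: "RAs will complete the checklist during initial recruitment and interim follow-up visits". On the repeat: "Site PIs will administer the fidelity checklist on 10% of the sample (approximately 3 patients per site". The Site PI looks at protocol adherence and at agreement with the RA. No numeric standard for agreement is given, and nothing says how the three patients are chosen.

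Under section 5.2 and the study procedures in section 6.1, the RA role also starts and stops the recording at in-person visits, registers the patient in HealthPAL and demonstrates access.

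The checklist has other content. Under section 17.1.1, reasons for low recruitment, refusal and loss to follow-up "will be gathered as part of the fidelity checklist". The paragraph on family members and caregivers in section 22.1 adds recording pauses and stops.

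On usual care (UC), section 5.1.2 says: "While patients in the UC group have no further in clinic procedures following baseline assessment". The sentence goes on to say that staff will attend UC visits when possible and offer the interpersonal-processes survey.

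AUDIO visits also leave records. Section 5.2 states: "The research team will maintain a copy of all recordings locally". Section 5.3 has the tablet recording transfer automatically to the cloud, and section 6.4.1 has HealthPAL register logins, listening and sharing.

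**The concern.** The next trial needs to know whether recordings are made, uploaded and made accessible as planned. The checklist is the plan's instrument for this, and for the delivery items it is largely a self-rating, because the RA role scores its own work. The Site-PI repeat is the only re-administration of the checklist in the plan. It is spread over both arms, although UC patients have no recording to deliver or receive. Some of the few checks may therefore fall on patients who cannot show whether audio delivery was over-scored.

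The unstated denominator adds to this. It can be settled after the data are seen, and the choice changes the AUDIO delivery rate that counts as meeting the target.

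**Working it through.** **Inputs.** There are 30 patients per site at three sites, 90 in all (section 26.0). Allocation is 1:1 in blocks of two within clinician (section 6.1), nominally 15:15 per site and 45:45 overall. The repeat covers 10%, about three patients per site (section 17.3.2). The target is above 90% (section 4.1).

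**1. The plan's own figure.** 0.10 × 30 = 3.0, which reproduces three per site. An AUDIO-only base would give 0.10 × 15 = 1.5, so the base is all patients at the site.

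**2. AUDIO patients among those checked, if selection ignores arm.**
- Expected per site: 3 × 15/30 = 1.5. Over three sites: 4.5 of 9.
- No AUDIO patient at a given site, simple random draw: C(15,3)/C(30,3) = 455/4060 = 0.112.
- Exactly one: 15 × C(15,2)/C(30,3) = 1575/4060 = 0.388. At most one: 0.500.
- None at one or more of three sites: 1 − (1 − 0.112)³ = 0.300.

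**3. Sensitivity to the split.** With 30 patients and six clinicians, the average is five per clinician, so blocks of two can end incomplete. If every clinician has exactly five patients, AUDIO numbers per site run from 12 to 18. The expected number checked is then 1.2 to 1.8, the chance of none at a site 0.20 to 0.05, and the chance of none at one or more sites 0.49 to 0.15.

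**4. What the checks could reveal.** The documents give no over-scoring rate. Assume RAs over-score a share r of AUDIO patients and the Site PI always sees it. The chance that nine checks include no such patient is (0.112 + 0.388p + 0.388p² + 0.112p³)³ for a draw that ignores arm, and p⁹ for an AUDIO-only draw, with p = 1 − r.

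| r | Draw ignores arm | All nine AUDIO |
|---|---|---|
| 10% | 0.63 | 0.39 |
| 20% | 0.39 | 0.13 |
| 30% | 0.23 | 0.04 |

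**5. AUDIO delivery rate needed to exceed 90%, by reading.**

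| Reading | Passes needed | AUDIO rate needed |
|---|---|---|
| Per patient, arms pooled, UC 45/45 | 82 of 90 (81/90 is exactly 90%) | 82 − 45 = 37; 37/45 = 82.2% |
| Per visit, two in each arm, UC all pass | 163 of 180 | 163 − 90 = 73; 73/90 = 81.1% |
| Per visit, two AUDIO and one UC, UC all pass | 122 of 135 | 122 − 45 = 77; 77/90 = 85.6% |
| Per patient, pooled, UC 43/45 | 82 of 90 | 39/45 = 86.7% |
| Per patient, pooled, UC 41/45 | 82 of 90 | 41/45 = 91.1% |
| Per patient, AUDIO only | 41 of 45 | 91.1% |

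With X ~ Binomial(45, true delivery rate), the first reading is met when X ≥ 37 and the last when X ≥ 41. At 82% true delivery the probabilities are 0.58 and 0.07; at 85% they are 0.77 and 0.17.

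**The case against.** A reader might infer that the target pools both arms and can therefore be met with AUDIO delivery at 82%. The documents do not say this. Section 4.1 gives no denominator, and if the checklist concerns audio delivery, treating UC patients as not applicable is at least as natural. The 82% needs three assumptions together: one pass or fail per patient, pooled arms and every UC patient passing. Appendix 16, the checklist itself, is listed but not in the text available here, and it may settle the scoring.

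A reader might also infer that UC patients have nothing to fail. That is too strong. They have a baseline assessment, follow-up windows whose deviations are reported (section 6.3) and contact after scheduled visits. Section 17.1.4 foresees UC patients recording their own visits. With UC at 41/45, pooling dilutes nothing.

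Audio delivery is also observed elsewhere: HealthPAL use data, a separate listening target above 70%, and self-report of not receiving a recording. Supervisor double-scoring of a staff checklist is an accepted design. Nothing bars Site PIs from choosing AUDIO visits, so the probabilities in steps 2 to 4 hold only for a draw that ignores arm.

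All of this stands, and it limits the point to a minor one. It does not change who scores delivery, the size and base of the repeat, or the absence of a selection rule. The HealthPAL and recording data are not linked to the fidelity score in the plan.

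**Conclusion.** The concern holds in a limited form. The RA role that delivers the recording also scores its delivery. The Site-PI repeat of three per site is sized on both arms and has no selection rule or numeric agreement standard. If selection ignores arm and the split is 15:15, about 4.5 of nine checked patients are AUDIO, with an 11% chance of none at a given site and 30% at one or more sites.

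The undefined target is a separate gap. The AUDIO rate it requires is about 81% to 91% depending on the reading, and the 82% figure is one conditional case, not a property of the plan.

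Severity is minor. Under section 17.1.1, falling short leads only to considering whether the protocol needs changing.

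**What to change.** Change sections 4.1 and 17.3.2, and carry the figure into 17.1.1:

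1. Report delivery and receipt of the recording against the target above 90% in the AUDIO arm, stating the scoring unit. Report UC protocol adherence separately.
2. Keep three Site-PI checks per site, but have the coordinating center select them at random from AUDIO visits. The expected number of AUDIO checks rises from 4.5 to 9. For baseline visits, release the selection only after allocation is revealed, so that it does not disclose the sequence.
3. Score items that leave a record (recording made, uploaded, access set up) from HealthPAL and the stored second copy for every AUDIO visit, in place of the RA's tick. Keep the RA checklist for items that leave no record.

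The cost is wording, some abstraction from systems already in use, and short notice for a Site PI when a baseline visit is drawn. The number of checks is unchanged and no new staff are needed. The downside is that UC procedures would no longer be independently observed by the Site PI, and the fidelity figure may come out somewhat less favourable.

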## **18.0 Provisions to Monitor the Data to Ensure the Safety of Subjects\***

Strategies to monitor, track and retain participants will be based on the research team's experiences of successfully conducting multi-site trials with older adults in primary care and guidance outlined by Thoma et al. Recruitment and Retention will be monitored by the research coordinator at Dartmouth, who will monitor enrollment, tracking of participants and retention of participants in REDCap across all sites. Reasons for loss (e.g., refusal, change in provider, death) to follow-up will be documented by the research assistant, reported to the Site PI immediately, and discussed at weekly PI Meeting, where mitigation plans will be considered.

While psychiatric or medical emergencies are very unlikely, they may be disclosed by participants during interactions with study staff. As such we have developed procedures for responding to psychiatric and medical emergencies and elevated levels of depression and anxiety, described in the Data Safety Monitoring Plan (see Appendix 17. DSMP). In any such case, the research assistant will follow up with the clinical team within 7 days to determine the patients continued involvement in the trial and document the outcome of the event.

**18.1 Monitoring enrollment:** Enrollment will be closely monitored on a weekly basis by an on-site research assistant and reported to the PIs and coordinators. The research assistant will review the electronic medical record (EMR) and calculate 1) the number of eligible patients scheduled to visit the clinic; 2) the proportion of eligible patients scheduled in the previous week who were successfully contacted and agreed to learn more about the project in clinic and 3) the proportion of patients who met with the research assistant and consented to take part in the project. Should the proportion of patients contacted who agree to learn more about the project (2) or proportion who agree to meet with the research assistant in-clinic and consent to take part drop below 60% the Site PI ([name], [name], [name]) will visit the clinic to observe study recruitment (both telephone call to invite patients to learn more about the project and in-

PROTOCOL TITLE: *The impact of sharing audio recorded clinic visits on self-management in older adults: a multisite trial*  
clinic consent). We will provide regular feedback on recruitment numbers to clinicians and clinic staff involved in the project, as well as weekly reports at the Steering Committee meetings.

**18.2 Tracking of participants.** The RA will review the EMR of participants and document in REDCap, scheduled patient visits (up to six months from recruitment). An RA will attend all scheduled visits of patients in the AUDIO group, to assist with recording visits as described above. Each Monday the RA will review the schedule of participating clinicians to confirm returning patients appointments. We will also use a tracking system within the EMR to alert the RA when a patient has scheduled a new appointment, which will be checked weekly by the RA.

**18.3 Retention of participants.** We have identified several strategies to boost retention. **1)** The RA will review the EMR of participants and document in REDCap, scheduled patient visits (up to six months from recruitment); **2)** patients will receive a tailored schedule, based on their preferences, of days and times that are best for follow up telephone calls; **3)** patients visiting the clinic within one-week of a planned follow-up assessment (T1, T2) will be met by the site research assistant and able to complete assessments in clinic if they wish; **4)** patients on the UC arm may be met in clinic by the RA if feasible during regularly scheduled interim visits; **5)** patients will provide the contact information of a family member or caregiver who could be contacted should they be unreachable **6)** patients will receive reminder letters a week prior to scheduled outcome assessments and **7)** Breuton et al. identified monetary incentives as the most effective way of increasing participant retention. Patients will receive honorariums to promote retention; a thank you note (Appendix 20. Patient Participant Thank You Note) will be mailed with \$30 (gift card or site-specific payment method such as Greenphire) following recruitment and \$20 (gift card or site-specific payment method such as Greenphire) upon completion of each follow-up assessment.

**18.4 Data and Safety Monitoring Board (DSMB).** A Data and Safety Monitoring Board (DSMB) will be appointed to provide additional oversight of the trial and will meet prior to recruitment to review the study protocol, Data Safety Monitoring Plan (DSMP; see Appendix 17), DSMB Charter (see Appendix 18) and at the end of data collection. PIs will attend these meetings, with minutes documented and any recommendations documented. Minutes and recommendations will be shared with the trial steering committee. The DSMB will consist of four members identified through the NIA standard approval process. The DSMB will then meet by WEBEX to review study progress annually throughout the project (approximately every 6 - 9 months). The DSMB will review enrollment and attrition rates and advise the PIs on any potential risks as well as on any risk mitigation plans. The DSMB recommendations will be discussed with the PIs as well as the Steering Committee. All data will be reviewed for protocol adherence, including a data verification check that the appropriate outcome measures are given at V 4.6 29June2022

PROTOCOL TITLE: *The impact of sharing audio recorded clinic visits on self-management in older adults: a multisite trial*

the appropriate time points. We do not expect any Serious Adverse Events (SAE) or Adverse Events (AE) in the trial that would require immediate reporting since there are no invasive procedures related to the interventions. If for any reason an SAE, AE or unanticipated problem were to occur, the DSMB would be immediately notified, as well as the sIRB at Dartmouth. The DSMB would convene by webinar within 72 hours and immediately review the Serious Adverse Events/Adverse Events and determine if in any way they were related to the research study. If an SAE or AE occur, a full review would be performed by the PIs, Steering Committee and the DSMB.

## 19.0 Provisions to Protect the Privacy Interests of Subjects

Before data collection starts, all study personnel will be required to undertake appropriate CITI coursework, including, but not limited to, HIPAA training and Good Clinical Practice. The MPIs and research staff will meet weekly by WEBEX, from the time of study award, to plan protocol implementation at each site. In month 6, a two-day 'kick off' training event will be hosted at Dartmouth College, and all study team members will join. During this training event, we will review and train research coordinators and assistants in all aspects of the study protocol including identification of patients, screening administration, recruitment and consent, survey administration and follow-up calls and plans for unexpected events. Additionally, patient recruitment will not begin until IRB approval is gained protocol, staff training occurs (including CITI certifications), and the trial is registered on ClinicalTrials.gov. We have extensive experience recruiting patients on to clinical trials and other projects. Participants will initially be contacted via a letter signed by their participating clinician to inform them about the project and given the option to opt out (Appendix 8. Recruitment Letter). Patients will then be contacted by phone by a member of the research team to further inform them about the research project and assess their interest in joining (Appendix 9. Telephone Patient Recruitment Script). This strategy was recommended by our patient partners as they reported it is easier to 'decline' participation in a study when speaking with a member of a research team vs. speaking with a clinician or member of the clinical team. Interested patients will arrive at the clinic early to allow time to complete consent processes and baseline assessment in an unhurried fashion. They will be informed of the data that is required (see 22.0 Consent Process) and will provide consent for the research team to access this data. They will be reassured that their data will be handled in confidence and maintained privately, and that neither their clinician or clinical team will have access to study data. Clear information will be provided on the study follow up schedule. Patients will be reminded that at any time, including after they leave the clinic, they can request to be removed from the project.

